### **4. STUDY SYNOPSIS**

#### **4.1 BACKGROUND AND RATIONALE**

Cardiovascular disease is the most common cause of death while on the kidney transplant waiting list and after transplantation. Current standard care involves screening for coronary artery disease prior to waitlist entry, then every 1-2 years, according to perceived risk, until transplanted. The aim of screening is two-fold. Firstly to identify patients with asymptomatic coronary disease to enable either correction, by bypass surgery or angioplasty, or removal of the patient from the list, with the ultimate aim of preventing premature cardiovascular mortality at the time of, or soon after kidney transplantation. Secondly, from a societal perspective, to prevent mis-direction of scarce donor organs into recipients who experience early mortality. This current screening strategy is not evidence based, has substantial known and potential harms, and is very costly. Two major issues of uncertainty require addressing in sequence: (1) whether to periodically screen asymptomatic wait-listed patients for occult coronary artery disease; and (2) whether to revascularise coronary stenoses in asymptomatic patients prior to transplantation. The CARSK study seeks to address the first of these 2 issues.

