Current CAD screening practice is not evidence based. Current transplant clinical practice guidelines recommend two phases of screening for CAD i) *prior* to acceptance onto the waiting list, *and* ii) screening at regular intervals (every 1-2 years) *after* wait-listing.(16) The aim of screening is to identify CAD by non-invasive tests (i.e. Exercise Stress test, Myocardial Perfusion Scintigraphy or Dobutamine Stress Echo or similar). Patients with abnormal non-invasive tests are typically removed from the waiting list and undergo coronary angiography followed by revascularization of any hemodynamically critical stenosis by coronary angioplasty with or without coronary stenting, or coronary artery bypass grafting. (16) Once the procedure is deemed successful and the patient recovered, they may be returned to the active transplant waiting list. Those with advanced, unmodifiable CAD are unlikely to have a survival benefit from transplantation and so are not listed, or if already on the list, are delisted. This strategy aims to promote survival peri-operatively and in the short-medium term after transplantation. From a societal perspective, it is also imperative to prevent mortality in the early post-transplant period as this also results in the loss of a donated kidney, which incurs an opportunity cost for those who remain on the waitinglist.

Although regular, non-invasive cardiac screening is the current standard of care, only 1 randomized single centre trial performed in 1992 has ever been performed to evaluate this strategy. (17) This study recruited 26 insulin dependent diabetic transplant candidates with coronary artery stenoses greater than 75%, atypical or no chest pain, and a left ventricular ejection fraction greater than 35%, and randomised them to medical therapy (calcium channel blocker plus aspirin) or revascularization

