**Does routine screening have other downsides?** Screening may paradoxically increase morbidity and mortality by: i) exposing patients to risk of angiography and revascularization procedures; or ii) by delaying or excluding patients from lifesaving kidney transplantation because of their perceived CAD status. In other settings, for example in most surgical candidates, screening is not beneficial. However, the goals of screening transplant candidates differ somewhat from other settings, and include not only prevention of peri-operative cardiac events, but also maintenance of transplant eligibility during wait-listing, and long-term post-transplant survival. The current standard of care may be harmful. The potential harmful outcomes related to the current strategy of screening and revascularization of asymptomatic transplant candidates are summarized in Table 1 below.

A recent joint Scientific Statement from the American Heart Association and the American College of Cardiology Foundation concluded “that there is no strong evidence for or against routine cardiac screening of asymptomatic transplant candidates” and that more evidence from randomized clinical trials was needed. The lack of evidence in the transplant setting has led to confusion about the optimal management of transplant candidates: the two major issues of uncertainty are whether to screen asymptomatic patients for occult CAD, and whether to revascularise coronary stenoses in asymptomatic, screen-detected patients.

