### 6.2 OUTCOME MEASURES

*Primary efficacy endpoint:* major adverse cardiac event (MACE), defined as any of the following: cardiovascular death, myocardial infarction, emergency revascularisation, hospitalisation for unstable angina.

*Primary safety endpoint:* the above MACE endpoint plus complications from cardiac diagnosis or treatment including major bleeding requiring transfusions or hospitalizations, vascular intervention subsequent to cardiac interventions stroke and all-cause death.

*Secondary endpoints:* death, cardiovascular death, procedure-related death, myocardial infarction, emergency revascularisation, stroke, hospitalisation with unstable angina, hospitalisation with heart failure, hospitalisation with arrhythmia, major bleeding, health-related quality of life (QoL), time off list (including number of temporary suspension and duration of each suspension), cost-effectiveness, incidence of permanent removal from list for cardiac causes; incidence of transplantation and cancellation of transplant due to CAD.

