### 10.3 STATISTICAL METHODS TO BE UNDERTAKEN

Efficacy outcomes will be analysed using intention to treat. A significance level of 5% shall be used for all analyses, unless otherwise specified. All analyses will be adjusted for site.

The primary analysis will be an analysis of the time to first occurrence of the primary outcome MACE, using a Cox model with treatment arm as a covariate and stratified by site. This analysis will provide an estimate of the HR, a p-value and CI. Non-inferiority will be claimed if the 95%CI of the HR lies entirely lower than an HR value of 1.25, with the screening arm being the referent group. Superiority will be claimed if the 95%CI lies entirely lower than 1. Proportional hazards assumption will be assessed using log-log survival plots and Schoenfeld residuals.

The outcome of all-cause mortality will also be analyse using a Cox model. The time to all other outcomes will be analysed using a competing risk model, with the competing risk being death. Outcomes which can occur more than once will also be analysed using an Andersen and Gill model (42). This model is a natural extension of the Cox model and unlike the Poisson or Negative Binomial models for count data, does not require the assumption of a constant event rate over time. Robust standard errors using the Sandwich estimator will be applied to ensure the correct p-value and CIs are calculated.

All time to event data will also be graphically summarised using a Kaplan Meier or cumulative incidence curves comparing the two treatment arms.

For all time to event outcomes, a subgroup analysis will conducted to test for a statistical interaction (effect modification) between treatment arm and transplantation. This will be performed by stratifying the survival models by transplant date and testing the HRs between the two strata.

Time off waiting list will be analysed using a negative binomial model, with an offset for total time in study.

Safety outcomes will also be analysed using both intention to treat and per-protocol approaches.

Balance between treatment arms will be assessed by comparing means for continuous variable characteristics, such as age, or by comparing proportion for categorical characteristics, such as sex. If there is any imbalance, then an adjusted analysis for any unbalanced characteristics will be conducted in addition to the analyses stated above, which only account for site.

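### Section 10.3 tests effect modification by transplantation, a post-randomisation endpoint that screening is expected to change, so the interaction p-value cannot separate effect modification from selection into transplant

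*Protocol*

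**What the plan says.** Protocol section 10.3 states: "For all time to event outcomes, a subgroup analysis will conducted to test for a statistical interaction" between treatment arm and transplantation. The method follows: "This will be performed by stratifying the survival models by transplant date and testing the HRs between the two strata". No separate level is given, so the general rule applies: "A significance level of 5% shall be used for all analyses, unless otherwise specified". Nothing in the section calls the analysis descriptive or notes that its strata form after randomisation.

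Elsewhere the protocol describes transplantation as follows:

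- **It comes after randomisation.** Section 8.2 requires that transplantation be expected more than 12 months after enrolment. Section 10.2 expects half of participants to be transplanted during the study.
- **It is an outcome.** Section 6.2 lists among the secondary endpoints "incidence of transplantation and cancellation of transplant due to CAD".
- **Screening is meant to act on it.** Section 4.1 gives as one purpose the finding of silent disease to allow either correction by revascularisation "or removal of the patient from the list, with the ultimate aim of preventing premature cardiovascular mortality at the time of" transplantation or soon after it.
- **The route runs through coronary status.** Section 5.2 says: "Patients with abnormal non-invasive tests are typically removed from the waiting list and undergo coronary angiography". Of patients with advanced, unmodifiable disease it says that they "so are not listed, or if already on the list, are delisted". It adds that screening may do harm "by delaying or excluding patients from lifesaving kidney transplantation because of their perceived CAD status". Table 1 reports an audit in which 45 of 130 candidates were held after abnormal tests, for a mean of 446 days.
- **Test results carry prognosis.** Sections 7.1 and 7.3 say that abnormal results on the two main tests predict cardiac events and death in renal failure.

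**The concern.** An interaction test is meant to show that the arm effect differs between groups that randomisation made comparable. These groups are formed by an event that occurs later and that one arm's strategy is designed to influence. If screening keeps some higher-risk patients from transplant, the transplanted patients in the screened arm are a lower-risk selection than those in the no-screening arm. A post-transplant HR above 1 (no screening against screening) could then be read as protection of recipients by screening, when it may only show who was allowed to become a recipient.

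At stake is a conclusion labelled as effect modification, with a p-value attached, on the question clinicians will ask next: does dropping screening matter more once a patient is transplanted? There is also a practical defect. The instruction covers all time-to-event outcomes, and for at least one of them it cannot be followed.

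**Working it through.** **1. What each stratum compares.** The natural reading of the text is that follow-up is split at the transplant date.

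- Before transplant: the comparison starts at randomisation with balanced arms. Patients leave it when transplanted. If the link between cardiac risk and transplant differs by arm, the remaining patients become progressively less comparable.
- After transplant: patients enter only if transplanted. This comparison is not randomised at any time.

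If patients were instead grouped as ever or never transplanted, immortal time would be added. No figure is relied on for that reading.

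**2. The mechanism in one formula.** Suppose a share p of patients would be held after screening, with R times the MACE risk of the others, and that screening keeps a fraction f of them from transplant in the screened arm only. With no true effect and timing ignored, the post-transplant HR is roughly

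[1 + p(R − 1)] ÷ {[(1 − p) + p(1 − f)R] ÷ [1 − pf]}.

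Take p = 45/130 = 0.346 from Table 1, and assume R = 2.5:

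- numerator: 0.654 + 0.346 × 2.5 = 1.519
- f = 0: 1.519 ÷ 1.519 = 1.00
- f = 1/3: 1.519 ÷ (1.231 ÷ 0.885) = 1.519 ÷ 1.391 = 1.09
- f = 2/3: 1.519 ÷ (0.942 ÷ 0.769) = 1.519 ÷ 1.225 = 1.24
- f = 1: 1.519 ÷ 1.000 = 1.52

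With R = 1 the result is 1.00 whatever f is. The documents give neither R nor f.

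**3. Simulations with a true HR of 1.00 before and after transplant, follow-up split at transplant.** The plan states no figure for this test, so there is none to reproduce. Both sets use N = 3306, 4 or 5 years of follow-up and about half transplanted. The strength of selection is assumed in both.

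*Set A: temporary holds.* MACE 8% per year on the list and 3% after transplant (section 10.2), 10% drop-out, hold of 446 days, hold starts spread over annual screens 1 to 3, and every held patient returns to the list.

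| Setting | Post-transplant HR | Rejects at 5% |
|---|---|---|
| Held patients at same risk | 0.99-1.00 | 5% |
| 45/130 held, screened arm only, risk 1.5-4 times | 1.01-1.14 | 5.1-9.5% |
| One third of the same patients also held in the other arm | 1.01-1.09 | 5.0-6.9% |
| Two thirds also held in the other arm | 1.00-1.05 | 5.0-5.5% |

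If instead every hold starts at month 12 and no transplant precedes month 12, a risk ratio of 4 with 45/130 held in the screened arm only gives 1.29-1.43 and 20-24%.

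*Set B: transplant rate graded by cardiac risk.* List hazard averaging 6% per year, post-transplant ratio 3/8 = 0.375, log-normal cardiac risk, 1,000 trials per setting.

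| Setting | HR before | HR after | Rejects at 5% |
|---|---|---|---|
| Same access in both arms | 0.99-1.00 | 0.99-1.00 | 4-5% |
| Screening delays all equally | 1.00-1.02 | 1.01-1.03 | 5-6% |
| Selective in screened arm, mild | 0.93-0.94 | 1.17-1.21 | 15-19% |
| Selective, moderate | 0.86-0.90 | 1.34-1.50 | 39-58% |
| Selective, strong | 0.81-0.85 | 1.54-1.85 | 69-89% |

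In the mild and moderate settings the arms' transplant proportions differ by only 1 to 2 points, so similar transplant rates would not rule the bias out. Set B grades access along the whole risk scale, so low-risk screened patients are transplanted sooner, which the protocol does not describe. It shows what strong selection would do, not what this trial will show.

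**4. What the test could detect (Set A inputs).** For 80% power at two-sided 5%, the detectable HR ratio is exp[(1.96 + 0.84) × SE].

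- Full follow-up, 67-113 post-transplant first MACE, SE 0.203-0.255: exp(0.568) = 1.77 to exp(0.714) = 2.04.
- Entry staggered over 36 months, 51-87 events, SE 0.233-0.292: exp(0.652) = 1.92 to exp(0.818) = 2.27.

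**5. Time to transplantation.** Section 10.3 sends every outcome other than MACE and death to a competing-risk model, so this endpoint falls under the instruction. After a time split, nobody in the post-transplant stratum is still at risk. With ever/never grouping, one stratum holds only events and the other none. Neither gives two HRs to compare. Under the time split the same is true of list removal and cancelled transplant.

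**The case against.** The strongest reply is that phase matters in this trial. Section 5.2 describes different risk before and after transplant and counts long-term post-transplant survival among the goals of screening, and the allocated difference applies only while patients are listed. No decision rule uses this test; non-inferiority and superiority rest on the overall Cox HR. Section 10.3 already calls it a subgroup analysis, and caveats may stand in a statistical analysis plan that is not shown. Screening could also lead to correction of disease and so to a genuine post-transplant difference. Nobody would fit a post-transplant HR for time to transplant; the word covering all outcomes is loose drafting.

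Much of this stands. The question is legitimate, which is why the estimates should be kept. The primary conclusion does not depend on the test. But a caveat elsewhere does not make the p-value a test of effect modification, and the possibility of a genuine difference is exactly what the test cannot isolate.

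The reply is also right about size. Section 5.2 notes that the tests do not necessarily identify plaques prone to rupture, and Table 1 says that only 5 of the 45 held patients were revascularised. Section 7.4 lets symptomatic patients in either arm be investigated, which would narrow the contrast. How far holds track MACE risk is therefore unknown.

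A reader might infer that both stratum HRs are equally unprotected. That goes too far: under a time split the pre-transplant comparison begins as the randomised one.

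**Conclusion.** The point holds as a matter of what may be concluded. On the protocol's own account transplantation is a post-randomisation endpoint through which screening works, so the planned p-value cannot separate effect modification from selection. For time to transplantation the test cannot be carried out.

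The size is not known. Rejection stays near 5% if transplant access does not depend on cardiac risk differently by arm. It is about 5-10% if all held patients return to the list with holds spread over time, and 15-89% under stronger assumed selection. Two inferences are tempting and neither is supported. One is that the test is known to have a high error rate: the selection strengths that produce one are assumed. The other is that the distortion is capped at a small value: the low figures need every held patient to return, whereas section 5.2 also describes delisting, and changing only the timing of holds and transplants gave 20-24%.

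Nor does this weaken the primary analysis. The intention-to-treat comparison, the 1.25 margin and the stated power are unaffected. In the Set B time-split runs the overall HR was 0.94-1.00. Any shift from 1 there arises because changing who is transplanted, and when, is itself an effect of the strategy, and the intention-to-treat HR properly includes it.

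The change should be made, although no primary conclusion turns on it.

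**What to change.** In section 10.3, replace the formal test with wording such as: Event rates and HRs by arm will be described separately for follow-up before and after the transplant date, with transplant as a time-dependent state. These are non-randomised comparisons and no interaction p-value will be given. They will not be produced for outcomes that can only occur before transplant.

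If a formal interaction test is wanted, it can use a baseline factor; diabetes is already a randomisation stratum (section 7.5). That would be an additional analysis and would not answer the question about transplant phase.

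The cost is two or three sentences, with no new data and no change to the primary analysis. What is lost is the before/after-transplant p-value, from a test with 80% power only for an HR ratio of about 1.8 to 2.3 under the assumed inputs. The descriptive HRs carry the same possible selection, so the non-randomised label has to stay with them wherever they are reported.

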**Table 1: Evidence of increased harm from CAD screening in ESKD**

Complications of revascularization are higher in people with ESKD				
Population	Event Type	Event Rate	citation	
U.S. Dialysis patients 1978-95	2year mortality post PTCA	52%	(23)	
	2year mortality post CABG	44%	(23)	
U.S. Transplant recipient 1995-99	2year mortality post PTCA	18%	(24)	
	2year mortality post CABG	17-26%	(24)	
Non-ESKD patients reported by Bari Investigators	5 year mortality post PTCA	14%	(25)	
	5 year mortality post CABG	12%	(25)	
2	Asymptomatic ESKD patients may be considered too high risk for surgery and excluded from transplantation rather than revascularized		(26)	
3	Screening prolongs waiting time prior to transplantation: Audit of 130 wait-list candidates in Canada found 45 were put on hold for transplantation because of abnormal screening tests for a mean of 446 days (only 5/45 were ever revascularized).			Audit for grant
4	Relative increased bleeding risk with use of anti-coagulation after revascularization in ESKD patients and most surgeons will not transplant anti-coagulated patients. In particular, clopidogrel is commonly prescribed for 6 months after coronary stent placement, but is a relative contraindication to transplant surgery.		(27)	
5	Angiography causes loss of residual kidney function. Preservation of residual kidney function is associated with increased dialysis survival		(28)	

PTCA= percutaneous coronary angiography, CABG= coronary artery bypass grafting

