## **10. STATISTICAL METHODS**

### **10.1 SAMPLE SIZE ESTIMATION & JUSTIFICATION**

The target total sample size is 3306 patients from 23 sites (7 from Australia, 1 from NZ, 15 from Canada). This number of sites will provide a target number of 1000 patients from Australia, 100 from New Zealand and 2206 from Canada. This equates to recruitment of  $\leq 4$  patients per month per centre. This rate is feasible given current wait-list and transplant volumes from all countries.

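### Time off the waiting list is a duration but is analysed with a negative binomial count model, so its model-based confidence interval is too wide by a factor that depends on an unstated time unit

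*Protocol*

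**What the plan says.** The outcome is listed among the secondary endpoints in Protocol sections 4.6 and 6.2 as "time off list (including number of temporary suspension and duration of each suspension". It therefore has two parts: a count of suspensions and a length of time.

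Section 10.3 gives one sentence of analysis: "Time off waiting list will be analysed using a negative binomial model, with an offset for total time in study". No time unit is stated, and no variance method is attached to this model.

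Earlier in the same section the Andersen-Gill model is preferred for recurrent outcomes because, "unlike the Poisson or Negative Binomial models for count data, does not require the assumption of a constant event rate over time". That paragraph ends: "Robust standard errors using the Sandwich estimator will be applied to ensure the correct p-value and CIs are calculated". The negative binomial sentence stands on its own further down.

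The only information on how this outcome is distributed is in Table 1, row 3. It reports an audit covering 130 Canadian candidates, of whom "45 were put on hold for transplantation because of abnormal screening tests for a mean of 446 days".

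**The concern.** A negative binomial model describes numbers of separate events. The number of suspensions fits that description; days off the list do not. Days off list pile up at zero, with values in the hundreds for those who were held. Fitted by maximum likelihood, the dispersion parameter is set largely by the zeros. It then overstates the variance of the mean, and the model-based standard error follows it. The model is also not invariant to rescaling: the same data in days, weeks or months give different dispersions, standard errors and p-values.

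Delay to transplantation is one of the routes by which section 5.2 and Table 1 say screening may do harm. If no screening proves non-inferior on MACE, less time off the list would be a main argument for adopting it. An interval that is too wide could hide a modest benefit. This point concerns the distribution and the standard error, not the choice of offset.

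**Working it through.** The protocol gives no power or interval width for this outcome, so it has no figure to reproduce.

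**Inputs from the protocol**
- Ever held: 45/130 = 34.6%; no hold: 85/130 = 65.4% (Table 1).
- Mean hold if held: 446 days, so the overall mean is 0.346 × 446 ≈ 154 days per candidate.
- Sample size: "The target total sample size is 3306 patients from 23 sites" (section 10.1).
- Follow-up: 5 years in Canada and 4 in Australasia (section 10.2).

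**Assumptions**
- 1:1 allocation, so 1653 per arm.
- Individual follow-up of 2.5-5 years in Canada and 2-4 years in Australasia.
- Exponential, lognormal or gamma hold durations, capped at follow-up.
- No site terms.

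**Simulation.** Each scenario used 100 simulated trials. The negative binomial was fitted by maximum likelihood with log total time as offset. Results for 34.6% held in both arms and exponential holds:

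| Unit | Fitted dispersion | Model SE | Sandwich SE | Empirical SD |
|---|---|---|---|---|
| Days | 16.56 | 0.142 | 0.070 | 0.071 |
| Weeks | 11.98 | 0.121 | 0.070 | 0.072 |
| Months | 8.26 | 0.101 | 0.070 | 0.065 |
| Years | 2.68 | 0.080 | 0.074 | 0.068 |

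**Hand check of the model SE.** With mean μ and dispersion α, SE ≈ √[2(α + 1/μ)/n per arm].
- Days: √[2(16.56 + 1/154.4)/1653] = 0.142.
- Weeks (μ = 22.1): √[2(11.98 + 0.045)/1653] = 0.121.
- Months (μ = 5.07): √[2(8.26 + 0.197)/1653] = 0.101.
- Years (μ = 0.42): √[2(2.68 + 2.37)/1653] = 0.078, close to the simulated 0.080.

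**Hand check of the true SE.** For a proportion p held with exponential durations, the squared coefficient of variation is 2/p − 1 = 2/0.346 − 1 = 4.78. That gives √(2 × 4.78/1653) = 0.076 before capping at follow-up. The simulated 0.070 corresponds to 0.070² × 1653/2 = 4.05. So the data carry a relative variance of about 4, while the fit in days uses about 16.6.

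**Ratio of model SE to sandwich SE**, across the three duration shapes at 34.6% held:
- Days 1.99-2.24.
- Weeks 1.69-1.90.
- Months 1.41-1.59.
- Years 1.04-1.08.

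In days, the nominal 95% interval covered the truth in 100% of simulated trials.

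**Sensitivity to the share ever held** (days, exponential): 20% gives 2.08, 50% gives 1.92, 70% gives 1.74 and 90% gives 1.40. With 34.6% against 20% held by arm, the days ratio is 1.93-2.17 across the three shapes.

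**What this does to a test.** With the null-case SEs above, significance needs an observed ratio below exp(−1.96 × SE):
- Days: exp(−0.278) = 0.76.
- Weeks: exp(−0.237) = 0.79.
- Months: exp(−0.198) = 0.82.
- Sandwich: exp(−0.137) = 0.87.

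A true ratio of 0.80 therefore falls short in days and clears the sandwich threshold comfortably. Simulated power at 34.6% held agrees:
- 20% reduction: about 10-15% in days and 40-55% in months, against 80-89% with robust errors.
- 30% reduction: about 68-80% in days, depending on the run.
- 50% reduction: 100% in days.

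**The case against.** Five points can be made for the plan.

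1. *Sandwich errors are already named in section 10.3.* If they applied here, the excess width would vanish and the unit would hardly matter (0.070 in days, weeks and months). But that sentence closes the Andersen-Gill paragraph, and nothing carries it over to the negative binomial model.

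2. *Unit and variance estimator are ordinary SAP content.* That is right, and silence on them alone would be no finding. What the protocol does fix is a count model for a duration. That choice makes the two open details decisive.

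3. *The audit is narrow.* It counts only holds for abnormal screening tests, in 130 candidates with no stated follow-up, whereas the endpoint is not limited to cardiac holds. All-cause holds would mean fewer zeros and a smaller excess. This stands, and it is why the size must be given as a range.

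4. *Large effects are still found.* A reader might infer that the planned analysis would usually miss a real reduction. The documents do not support that. They state no expected effect, and if most such holds come from abnormal screening tests, removing routine screening could cut them sharply. The loss is serious only for effects near 20%.

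5. *The error is conservative.* With no true effect, the model-based test rejected at most about 1% of the time in days, weeks and months. False-positive claims are not inflated, and the primary MACE and safety conclusions are untouched. This also stands.

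**Conclusion.** The concern holds in a limited form. Section 10.3 commits a duration with many zeros and long holds to a count model, with no unit and no robust variance. Under the audit figures, 1653 per arm and 2-5 years of follow-up, the model-based standard error is too large by about 2.0 in days, 1.7-1.9 in weeks, 1.4-1.6 in months and near 1 in years. In days it falls to about 1.7 at 70% ever held and 1.4 at 90%.

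Two stronger readings should be avoided. A flat statement that the interval is twice too wide is not a property of the protocol text: it needs days, model-based errors and roughly half or fewer participants ever held. Nor do the documents describe only a few long holds, since 35% of audited candidates were held.

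The consequence is lost precision on one secondary outcome and a p-value that depends on an arbitrary unit. The change is worth making because the outcome bears on the case for stopping screening and the correction is cheap.

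**What to change.** In section 10.3 and the SAP:

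- Keep the negative binomial model for the number of suspensions.
- For total time off list, fix the unit as days and estimate the ratio of mean time off list, adjusted for site.
- Take the confidence interval from sandwich standard errors or a participant-level bootstrap.

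A log-link quasi-Poisson mean model would suit, but robust errors on the existing mean model are enough. If the sponsor already intends the sandwich estimator here, saying so is most of the correction. The cost is one sentence in each document, with no new data and no change to the sample size.
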